8 STUDY POPULATION

8.1 PATIENT ACCOUNTABILITY

8.1.1 Treatment Compliance

At each study visit, all study drug returned by the subject (used and unused) will be collected and new study drug will be dispensed. The appropriate study personnel must document the number of used and unused ampoules and determine within the interactive voice/web response system.

Subject compliance with the prescribed dosage regimen will be monitored throughout the study. If it is determined that a subject is not compliant with study drug, the site personnel must re-educate the subject on proper dosing compliance and its importance.

Treatment compliance will be presented as a table summarizing the counts and summary statistics for used and unused ampoules by the assigned treatment.

8.1.2 Protocol Deviations

Significant protocol deviations occurring during the study, either critical or major, that could impact the completeness, accuracy, and/or reliability of the study data or that may affect a subject's rights, safety, or wellbeing will be determined by the Sponsor (which will be completed prior to database lock) and will be presented for all subjects randomized.

8.2 ELIGIBILITY CRITERIA

Males and females, 18 years of age and above at the time of informed consent, who have been diagnosed with WHO Group 3 PH associated with COPD are eligible for randomization to this study. A full list of inclusion and exclusion criteria can be found in the study protocol, Sections 4.1 and 4.2.

8.3 OTHER DESCRIPTIONS OF STUDY POPULATION

All summaries of baseline information will be based on the full analysis set population, unless otherwise noted.

8.3.1 Demographics

Descriptive statistics will be presented overall based on the overall population for the following demographic data collected prior to randomization:

- age (in years);
- age (<65, ≥65 years);
- sex (males, females);
- race (White, Black or African-American, Asian, American Indian or Alaskan Native, Native Hawaiian or Other Pacific Islander);
- ethnicity (Hispanic or Latino, non-Hispanic or Latino);
- baseline (Screening Visit 1 and Day 1) weight (in kg);
- baseline (Screening Visit 1) height (in m);
- baseline (Screening Visit 1 and Day 1) Body mass index (BMI) (in kg/m²);
- country of clinical site (USA, Israel, Argentina).

8.3.2 Baseline Disease Characteristics

Descriptive statistics will be presented overall based on the randomized population for the following disease characteristics collected prior to randomization:

- age of WHO Group 3 PH-COPD diagnosis (date of diagnosis minus date of birth, in years, by quartiles);
- years of PH-COPD (date for the start of low dose run-in minus date of diagnosis, in years, by quartiles);
- baseline (Day 1) 6MWD;
- baseline (Day 1) Borg dyspnea score;
- baseline (Day 1) 6MWD and Borg dyspnea composite score;
- baseline (Days -7 to -1) actigraphy: average minutes of overall activity and MVPA;
- baseline (Day 1) SGRQ score;
- baseline (Day 1) UCSD SOBQ score;
- baseline (Day 1) plasma concentration of NT-proBNP;
- baseline (Screening Visit 1 and Day 1) FEV₁;
- baseline (Screening Visit 1 and Day 1) FEV₁/FVC;
- lowest recorded SpO₂ during baseline (Screening Visit 1 and Day 1) 6MWT;
- baseline (Day 1) PGA: categorical percentages and average scale value for fatigue and shortness of breath;
- baseline (Day 1) DSP;

- supplemental oxygen use and flow rate (in L/min) with 6MWT at baseline (Screening Visit 1 and Day 1);
- At-home spirometry values at baseline (Day 1).

8.3.3 Medications

Prescription or nonprescription medications (including vitamins and herbal products) will be coded using the most recent version of the WHO-Drug Global Dictionary prior to the data base lock.

Medications will be summarized overall and by assigned treatment - 1 for prior medications and 1 for concomitant medications. The number and percentage of subjects with any medication will be summarized by decreasing order of incidence. The number and percentage of subjects who have taken a medication within a primary drug category will be summarized by cohort under that drug category by the most specific level available.

For these summaries, a subject taking the same medication multiple times will only be counted once for the corresponding most specific level available. Similarly, a subject who took multiple medications within the same drug category will be counted only once for that drug category. Prior and concomitant medications will be presented in alphabetical order of drug category; within each drug category, the most specific level available for drugs will be presented in decreasing order of incidence.

8.3.3.1 Prior Medications

All medications or therapies reported before the first dose of treprostinil (during low dose run-in) are defined as prior medications and will be summarized overall and by assigned treatment.

8.3.3.2 Concomitant Medications

Any medication or therapy initiated after, or corresponding with, the first dose of treprostinil (during low dose run-in) will be considered a concomitant medication. These medications will be presented using the same structure as prior medications. Tabulations will allow occurrences during low dose run-in and blinded treatment to be assessed (eg, low dose treprostinil, treprostinil treated, any treprostinil, placebo treated).

8.3.4 Medical History

Medical history identified prior to ICF date will be summarized overall and by treatment. The number and percentage of subjects with any occurrence will be summarized by System Organ Class (SOC; alphabetically) and by Preferred Term (PT) in decreasing order of incidence.

For subjects experiencing the same medical condition multiple times, the summaries will count the condition only once for the corresponding PT. Similarly, the summaries will count a subject with multiple medical conditions within the same SOC only once for that SOC. SOCs will be tabulated alphabetically; within each SOC, PTs will be presented in decreasing order of incidence.

Medical conditions are coded according to the Medical Dictionary for Regulatory Activities (MedDRA) coding dictionary. The most recently available MedDRA version before the database lock date will be used to assign PTs and SOCs (the database will document the version at time of data lock).

8.3.5 Subject Disposition

All subjects screened will be used to describe subject disposition. The number and percentage of randomized subjects who completed and who discontinued (with reason for discontinuation) will be summarized overall and by treatment sequence at the time of discontinuation. In addition, the summary table will display the number and percentage of subjects in each of the following groups, as well as the reason for discontinuation and treatment assigned, where applicable:

- Screened, but never randomized;
- Randomized, but never treated;
- Discontinued during the first treatment phase;
- Completed the first treatment phase and discontinued prior to the second;
- Completed the first treatment phase and discontinued during the second treatment phase;
- Completed the study (both treatment phases).

A CONSORT diagram (Schulz 2010) may be used to display the disposition by treatment.

9 EFFICACY ANALYSES

The following describes the planned primary endpoint analysis using 6MWD if the alternative primary endpoint analysis is not enacted. For details about the alternate primary endpoint and analysis, see Section 9.2. All efficacy analyses will be performed on the FAS (see Section 8). Additional supportive analyses will be conducted on the PPROT, as outlined below.

9.1 PRIMARY EFFICACY MEASURE

The primary efficacy endpoint is the change in 6MWD measured at peak exposure (defined as 10 to 60 minutes after dosing) after 12 weeks of study drug treatment. The primary endpoint analysis will evaluate the difference in baseline-adjusted 6MWDs between active and placebo conditions. The primary endpoint analysis will test the hypothesis of an improvement in baseline-adjusted 6MWDs for active compared to placebo treatments, as randomized, to subjects with PH-COPD. The primary null hypothesis to be tested is that there are no differences in the baseline-adjusted means change in 6MWDs between active and placebo treatment groups.

9.1.1 Hypothesis Test

The analysis of the primary efficacy endpoint of peak 6MWD assesses if inhaled treprostinil will increase the distance traversed in the peak 6MWT at Week 12 relative to baseline compared to placebo in subjects with PH-COPD. The null and alternative hypotheses are:

$$H_0: \mu_1 = \mu_2$$

$$H_a: \mu_1 > \mu_2,$$

where μ_1 and μ_2 are the baseline-adjusted change from baseline in 6MWD of the inhaled treprostinil and placebo treatments, respectively.

9.1.2 Primary Efficacy Analysis Data

The primary efficacy analysis will be based on all available measurements of the 6MWD for the FAS as observed in the study, with the exception that for subjects whose 6MWD measures at Week 6 or Week 12 of either Period are missing due to death or being too ill to perform 6MWT, the missing values will be imputed as the worst possible score (0 meter) and change-from-baseline scores calculated. For missing data due to any other reason, the missing value will not be imputed.

9.1.3 Primary Efficacy Analysis

Descriptive statistics showing the raw values and changes from baseline for the 6MWD will be presented for each scheduled visit by treatment. Additionally, boxplots presenting the raw values and changes from baseline for each visit for the 6MWD may be presented.

A mixed-effect model for repeated measures (MMRM) will be used to estimate the treatment effect. The magnitude of treatment effect will be compared between the 2 treatments across the 12-week treatment periods, and the test of the Week 12 change from baseline and difference between treatments will be produced using contrasts.

[REDACTED]

- [REDACTED]
- [REDACTED]
- [REDACTED]
- [REDACTED]
- [REDACTED]
- [REDACTED]
- [REDACTED]

[REDACTED]

[REDACTED]

[REDACTED]

- [REDACTED]
- [REDACTED]
- [REDACTED]
- [REDACTED]
- [REDACTED]
- [REDACTED]

Least square means for baseline adjusted 6MWD for each treatment group, difference of LS means between treatment groups with the associated p-value, and 95% CIs for each treatment LS mean and the difference in LS means will be summarized and presented.

9.1.4 Sensitivity Analyses

Sensitivity analyses will be carried out to assess the effect of deviations from the study protocol, the carryover effect, and the impact of missing data. All analyses will be based on the data as described in Section 9.1.2, unless otherwise noted. These analyses are mandatory if the primary endpoint analysis is statistically significant, but will otherwise be performed at Sponsor’s discretion.

9.1.4.1 Deviations from Protocol

A “per protocol” analysis will be carried out to assess the effect of substantive deviations from the study protocol. Analyses will be identical to those in Section 9.1 for the primary analysis, except the PPROT analysis population will be used instead of the FAS (ie, the dataset used will remove subjects with substantive deviations). The test will examine the robustness of the total treatment effect to known departures from the protocol. The magnitude of the treatment effect and significance testing will be contrasted against the results from the primary efficacy analysis.

If results are generally similar, then the effect of substantive deviations will be considered minimal.

9.1.4.2 Carryover Effect

The carryover effect analysis will be performed using a 2-sided Wilcoxon Rank Sum Test on the sum of the changes in 6MWD for each treatment period between assigned treatment sequences. To determine the sum of the treatment effects, the change in the 6MWD from Baseline to Week 12 for the active treatment and placebo will be summed for each subject. The test will determine if the total treatment effect is different across assigned treatment sequence groups. If the result is statistically significant, the assumption that the washout period was long enough to rule out the carryover effect, will be examined using the following approach:

[REDACTED]

[REDACTED]

9.1.4.3 Multiple Imputation for Missing Data Due to Death and Too Ill to Walk

The primary efficacy analysis will be imputed 6MWD observations missing due to death or being too ill to perform 6MWT as the worst possible score (0 meters) and change scores calculated. An alternative sensitivity analysis will be conducted that imputes missing observations due to death or being too ill to perform 6MWD to be the worst observed change score in all subjects plus a random error component added. The error will be randomly drawn from a normal distribution with a mean of 0 and a variance equal to the residual variance estimated from the mixed model for observed values of change from baseline in 6MWD, adjusted for the same covariates and factors as pre-specified for the primary analysis.

This analysis will be identical to those in Section 9.4 for the primary analysis, except for the use of the alternatively imputed data for death or being too ill to perform 6MWT as described above.

The test will examine the robustness of the total treatment effect to an alternative imputation strategy for handling missing data arising from death or being too ill to walk.

9.1.4.4

[Redacted]

- [Redacted]

- [Redacted]

- [Redacted]

[Redacted]

- [Redacted]

- [Redacted]

- [Redacted]

- [Redacted]

- [Redacted]

- [Redacted]

- [Redacted]

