#### 4 SUBJECT ELIGIBILITY

# 4.1 INCLUSION CRITERIA

Subjects who meet the following criteria may be included in the study:

- 1. Voluntarily gives informed consent to participate in the study.
- 2. Males and females 18 years of age and above at the time of informed consent.
  - a. Females of childbearing potential (defined as less than 1 year postmenopausal and not surgically sterile) must agree to practice abstinence or use 2 highly effective methods of contraception (defined as a method of birth control that results in a less than 1% per year failure rate, such as approved hormonal contraceptives, barrier methods [condom or diaphragm] used with a spermicide, or an intrauterine device) for the duration of study treatment and for 48 hours after discontinuing study drug. Subjects must have negative pregnancy tests at Screening Visit 1 (urine [prior to the first dose of study drug] and serum) and the Baseline Visit (urine [Study Week 1]).
  - b. Males with a partner of childbearing potential must agree to use a barrier method (condom) with a spermicide for the duration of treatment and for at least 48 hours after discontinuing study drug.
- 3. Diagnosis of PH-COPD (WHO Group 3).
- 4. Clinical diagnosis of COPD per the Global Initiative for Chronic Obstructive Lung Disease (GOLD) diagnostic criteria (2020) and documented spirometry parameters measured during Screening Visit 1 (prior to start of low dose inhaled treprostinil), as follows:
  - a. FEV1 <80% predicted
  - b.  $FEV_1/FVC < 70$
- 5. Resting SpO2 ≥90% during Screening Visit 1, with or without supplemental oxygen, and supplemental oxygen cannot exceed 10 L/min by any mode of delivery.
- 6. A 6MWD ≥100 meters during Screening Visit 1 (prior to start of low dose inhaled treprostinil).

- 7. Willing to undergo RHC during Screening Visit 1. An RHC performed within 12 months prior to the start of Screening Visit 1 is acceptable for determining eligibility, even if done without oxygen or vasodilator challenge, and a repeat RHC is not required. The following parameters must be documented for eligibility:
  - a. PVR >4 Wood units
  - b. Pulmonary artery wedge pressure (PAWP) or left ventricular end-diastolic pressure (LVEDP) of ≤15 mmHg
  - c. PAPm of ≥30 mmHg
- Must be on a stable and optimized dose of chronic COPD medications for ≥30 days prior
  to the start of Screening Visit 1 and remain on the same dose throughout the Screening
  Period.

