#### 10.2 SAMPLE SIZE

This is an adaptive design study that will be initiated as a crossover study (the **Original Crossover Design**). However, due to the uncertainty of clinical benefit with inhaled treprostinil exposure in PH-COPD subjects and the ongoing COVID-19 pandemic, there is a possibility of treatment discontinuations and/or missing data due to COVID-19 impeding onsite visits, which may render estimates for efficacy outcomes inefficient or biased, thus an automatic switch to the **Contingent Parallel Design** or an alternative primary endpoint that has been incorporated in this study protocol. The protocol specifies the algorithm to seamlessly transition to a parallel-group design (**Contingent Parallel Design**) if the degree of missing data subsequent to subject treatment crossover is not tolerable for primary analysis.

Similarly, this protocol specifies the algorithm to switch the primary endpoints to measurements conducted remotely if the COVID-19 pandemic prevents onsite visits and data collection for the intended primary endpoint data. Evaluations of missing data will be performed in a blinded fashion at the conclusion of the study, irrespective of actual efficacy outcomes and any information regarding efficacy outcomes prior to crossover and, as such, will not impact the Type I error rate (FDA Guidance 2019). Section 10.2.1 presents the adaptation procedures to be employed for this protocol.

The **Original Crossover Design** is a 2x2 crossover study designed to have 90% power to detect a placebo-corrected mean change from baseline difference of 30 meters, assuming that the standard deviation of differences is 85 meters and using a 2-group t-test with a 0.01 two-sided significance level, with a sample size of 124 subjects (62 in each sequence group). To account for a discontinuation rate of approximately 10%, the total sample size will be approximately 136 subjects.

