Based on published data using actigraphy as an outcome measure in studies conducted in the pulmonary hypertension population (Gonzalez-Saiz 2018; Nathan 2020), reasonable statistical power (80%; 2-sided alpha of 0.05) can be assumed for approximately 90 evaluable subjects when the observed improvement is in excess of 6%-8% for overall activity or 20-25% or greater for moderate to vigorous activity. Nathan (2019) provides that the clinically meaningful difference observed in their study was 5% to 10% for overall activity and 20% for MVPA, with a clinically meaningful difference range in studies of COPD patients from 11% to 29%.

The Contingent Parallel Design is a parallel-group study designed to use an allocation ratio of 1:1 between inhaled treprostinil and placebo, with a sample size of 266 subjects (133 per treatment) that would provide at least 90% power at a significance level of 0.05 (2-sided hypothesis) to detect a 30-meter between-treatment difference in the change from baseline in 6MWD, assuming a standard deviation of 75 meters. To account for a discontinuation rate of approximately 15%, the total sample size will be approximately 314 subjects.

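### The death/too-ill sensitivity analysis in SAP 9.1.4.3 has no floor, so it can impute a change worse than the plan's own worst possible score of 0 m

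*SAP*

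**What the plan says.** SAP 9.1.2 sets the primary rule for 6MWD missing at Week 6 or Week 12 because of death or being too ill to walk: "the missing values will be imputed as the worst possible score (0 meter) and change-from-baseline scores calculated". The imputed change is therefore minus the subject's own baseline.

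SAP 9.1.4.3 repeats that 0 m is the worst possible score and then describes a sensitivity analysis with a different rule. Walks missed through death or being "too ill to perform 6MWD to be the worst observed change score in all subjects plus a random error component added" get one common centre, whatever the baseline. On the error it says: "The error will be randomly drawn from a normal distribution with a mean of 0 and a variance equal to the residual variance" from the mixed model for observed changes. The readable text of 9.1.4.3 states no floor, truncation or cap. The blacked-out text is in part of 9.1.4.2 and in 9.1.4.4.

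SAP 9.1.4 makes the sensitivity analyses mandatory if the primary result is significant. Protocol 4.1 allows low walkers into the trial: "A 6MWD ≥100 meters during Screening Visit 1 (prior to start of low dose inhaled treprostinil").

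**The concern.** If 0 m is the worst possible walk, the worst possible change is minus the baseline. A common change plus unbounded error ignores that limit. For a subject with a low baseline, the analysis can impute something worse than the 0 m used in the primary analysis. For a subject with a high baseline, it imputes a substantial positive walk.

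The stated purpose is to test robustness to another way of handling death and illness. A reader of the result should know whether the alternative is harsher or milder than the primary rule. As written it is harsher for some subjects and milder for others, and part of the harsher side lies outside the range of the measurement.

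**Working it through.** **The plan's own figures, which supply the scale.** The crossover is sized for "90% power to detect a placebo-corrected mean change from baseline difference of 30 meters", with a "standard deviation of differences is 85 meters and using a 2-group t-test with a 0.01 two-sided significance level" and "a sample size of 124 subjects (62 in each sequence group") (Protocol 10.2).

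- Noncentrality = 30 / (85/√124) = 30/7.633 = 3.93 on 122 df. Power is 0.903; at N = 122 it is 0.898. The stated 124 is reproduced.
- Dropout: 124 × 1.10 = 136.4, against about 136 stated.
- The parallel design is sized "assuming a standard deviation of 75 meters". Power at 133 per arm is 0.901, and 266/0.85 = 313 against 314 stated.

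The SD of change per period is therefore about 85/√2 = 60 m if the two periods' changes are independent, or 75 m on the parallel assumption.

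**Formula.** Let B be the baseline, W the worst observed change (negative), and e ~ N(0, s²). The imputed change is W + e and the implied walk is B + W + e, so

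P(walk < 0) = Φ((|W| − B)/s).

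This is at least 50% whenever B ≤ |W|, whatever s is.

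**By baseline, for an assumed W = −200 m:**

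| Baseline (m) | P(walk < 0), s = 60 | P(walk < 0), s = 75 | P(walk > 100 m), s = 75 |
|---|---|---|---|
| 100 | 95% | 91% | 0.4% |
| 200 | 50% | 50% | 9% |
| 250 | 20% | 25% | 25% |
| 300 | 5% | 9% | 50% |
| 350 | 0.6% | 2% | 75% |
| 400 | <0.1% | 0.4% | 91% |

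**Across subjects.** W, the residual variance and the baseline distribution are not in the documents, so this step rests on assumptions: mean change zero, two visits per subject-period, within-subject correlation 0.5, and baselines normal with SD 90 m truncated at 100 m. The 100 m limit applies at Screening Visit 1, so it is only a guide to the Day 1 baseline. W is simulated and the same SD is used for W and for the error.

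| Assumed baseline location (m) | SD 60 m, 272 subject-periods, W ≈ −183 m | SD 75 m, 314 subjects, W ≈ −232 m |
|---|---|---|
| 200 | 36% below 0 m | 55% below 0 m |
| 250 | 24% | 41% |
| 300 | 14% | 28% |
| 350 | 6% | 16% |

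Two variations:

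- Simulated observed walks kept above 0 m, with 124 subjects, two or four visits each, and baseline means of 200 to 350 m (SD 60 to 100 m): W averages −161 to −220 m, and 6% to 49% of implied walks are below 0 m.
- A smaller residual SD of 42 to 53 m for the error: 5% to 56%.

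**The other end.** With SD 60 m throughout, 13%, 24%, 39% and 56% of implied walks exceed 150 m at locations 200, 250, 300 and 350 m. This comes mainly from the common W: at W = −183 m, a subject with a 450 m baseline is centred on 450 − 183 = 267 m.

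**The case against.** The strongest reply is about consequence. The model analyses change, so a negative walk is implied (baseline + change) and never entered. The rule is the same for both treatments. This is one sensitivity analysis, required only after a significant primary result. Its declared aim is an alternative imputation strategy, so differing from 0 m is intended, and mean-zero error is an ordinary way to add variability. The documents give no number of deaths or too-ill subjects, so no shift in the treatment contrast can be computed. All of this stands and limits the size of the point. It does not remove the conflict between the rule and a worst possible score that the same section states.

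Scope is also uncertain. SAP Appendix 12.4.5 supplies new text for Section 9.1.4 under the Contingent Parallel Design and defers the planned sensitivity analyses to an addendum. Whether 9.1.4.3 carries over is not explicit.

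A reader might infer that this undermines the most influential imputation in the trial, that low-baseline subjects are the ones most likely to die, or that comparison with the primary result reflects baselines and not robustness. The documents contain nothing to support any of these. A reader might also object that symmetric error puts half of the imputed changes above the worst observed one. That is true for any W and s, but the SAP does not promise a score at or below the worst observed.

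**Conclusion.** The rule in SAP 9.1.4.3 is faulty as stated: followed exactly, it allows changes below minus baseline. That part, and the 50% result for baselines at or below |W|, needs no assumption beyond the SAP text.

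The overall share is supportable only as a range, roughly 6% to 55% of implied walks below 0 m. It is 6% to 36% with SD 60 m throughout and 16% to 55% with SD 75 m, for baseline locations from 350 m down to 200 m. It would go too far to say that about half of the imputed walks are negative: that needs low baselines and the larger SD together.

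The primary test and its error rate are unaffected. The loss is in the clarity of the robustness check.

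**What to change.** In SAP 9.1.4.3, set

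imputed change = max(−baseline, worst observed change + error),

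so that no imputed value is worse than the primary analysis's 0 m. State that the worst observed change comes from measured walks only, excluding the 0 m imputations of 9.1.2. This matters because 9.1.4 bases its analyses on the 9.1.2 data.

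Describe the result as a milder alternative to the 0 m rule. With the floor it is never harsher, and the common worst change still credits high-baseline subjects with positive walks. As an illustration, take W = −200 m, s = 75 m and baseline mean 300 m (SD 90 m). The share below 0 m goes from 19% to none and the mean imputed change from −200 to −189 m, against −303 m under the 0 m rule.

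The cost is a sentence or two in the SAP and one line of code, with no new data. The downside is some loss of spread in the imputed values, larger where baselines are low.

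Capping the draw at the worst observed change is optional. It discards half of the intended variability and does not remove the long walks: at location 300 m, about 14% (SD 75 m) to 29% (SD 60 m) of imputed subjects would still be above 150 m.
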